#### Medtronic Controlled Information

## 11 Adverse Events and Device Deficiencies

### 11.1 Definitions/Classifications

An AE is any untoward medical occurrence that does not necessarily have to have a causal relationship with this treatment. An AE can therefore be any unfavorable and unintended sign (e.g., abnormal laboratory finding, symptom, or disease temporally associated with the use of a product, whether or not considered related to the product(s) under study. This definition includes events related to the procedures involved and/or worsening of pre-existing conditions. Pre-existing conditions for which the condition has not worsened, will not be reportable as an adverse event.

AEs are intended to be volunteered by patients or observed by the investigator and are to be recorded as appropriate within the electronic data capture (EDC) database. Each event will be classified according to the criteria defined in this protocol. If possible, a specific diagnosis should be recorded rather than a listing of individual signs and symptoms. AE reporting processes will be carried out in compliance with the protocol, the governing IRB, and the requirements of FDA and other applicable regulatory authorities.

#### 11.1.1 Severity of Adverse Events

The severity of adverse events should be assessed according to the World Health Organization (WHO) Recommendations for Grading of Acute and Subacute Toxic Effects. The following definitions should be used for events that are not defined in the WHO Toxicity Scale.

**Mild (Grade 1):** The adverse event is noticeable to the subject but does not interfere with routine activity. The adverse event does not require removal of the implant(s).

**Mild (Grade 2):** The adverse event interferes with routine activity but responds to symptomatic therapy or rest. The adverse event does not require removal of the implant(s).

**Severe (Grade 3):** The adverse event significantly limits the subject's ability to perform routine activities despite symptomatic therapy and may require hospitalization. In addition, the adverse event may require removal of the implant(s).

**Life-threatening (Grade 4):** The adverse event requires removal of the implant(s), or the subject is at immediate risk of death, even if not related to the implant(s).

Medical and scientific judgement should be exercised in deciding whether expedited reporting is appropriate in other situations, such as important medical events that may not be immediately life-threatening or result in death or hospitalization but may jeopardize the patient or may require intervention to prevent one of the other outcomes listed in the definition above.

An Adverse Event that is of Grade 3 or Grade 4 will be considered a serious adverse event (SAE). All serious adverse events (SAEs) should be reported immediately to the Sponsor. The immediate

---

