## 11.1.3 Secondary Surgical Interventions

Some AEs or treatment failures may lead to a secondary surgical intervention at an operated index level. Information on the types of secondary surgical interventions is provided in the section below. Secondary Surgical Interventions will be classified by Medtronic. All patients undergoing a secondary surgical intervention at any operated index level will be followed.

- **Revision:** A procedure that adjusts or in any way modifies either one or both of the original implant configurations (e.g., adjusting position of the original configuration, removal with replacement with the same type of study implant). A revision will be classified as a treatment "failure".**Removal:** A procedure that removes one or more components of the original implant configuration without replacement with the same type of trial implant. Removals will be classified as either elective or non-elective. An elective removal is a procedure that removes the Prestige LP™ Cervical Disc(s) at the discretion of the investigator and/or the patient. An elective removal will not be classified as a treatment "failure." An elective removal is not considered an SAE. A non-elective removal is any removal other than an elective removal and is considered an SAE and will be classified as a treatment "failure."

NOTE: In the event that an implant requires a removal (explant), specific information and instructions are to be followed for this process. The instructions and information regarding the process is provided in the "Procedure for Retrieval, Handling and Packaging" included as an attachment to this protocol in **Appendix II**. All explanted devices will be analyzed along with histological evaluation of any retrieved peri-prosthetic tissue under the Post-approval Device Failure study (Explant Analysis) for the two-level indication.

- **Supplemental Fixation:** A procedure at the involved level(s) in which additional spinal devices not approved as part of the protocol are placed. A supplemental fixation will be classified as a treatment "failure."
- **Reoperation:** Any surgical procedure at the involved level(s) that does not remove, modify, or add any components and is not considered a removal, revision, or supplemental fixation. A reoperation, elective removal or other surgical procedure will not be classified as a treatment "failure."
- **Other:** Any surgical procedure not classified as a revision, removal, supplemental fixation or reoperation.

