7.8.2.1 Overall Success

Overall success is claimed when the following four conditions are met:

- Postoperative NDI score improvement of at least 15 points from preoperative;
- Maintenance or improvement in neurological status;
- No serious, implant or implant/surgical procedure associated adverse event; and
- No secondary surgical procedure classified as “failure”.

Frequency and percentage of overall success at postoperative time points will be summarized, and no statistical conclusion will be drawn.

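### Protocol 11.1.1 makes severity Grade 3 or 4 its only general test for a serious adverse event and points to a list of outcomes it does not contain, so a lower-grade event with such an outcome is not automatically serious

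*Protocol*

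**What the plan says.** Protocol 11.1.1 asks for severity to be graded on a WHO toxicity scale. Its own four grades apply to events that scale does not define.

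- **Grade 2:** "The adverse event interferes with routine activity but responds to symptomatic therapy or rest". Grades 1 and 2 both exclude a need to remove the implant.
- **Grade 3:** the event "significantly limits the subject's ability to perform routine activities despite symptomatic therapy and may require hospitalization". Removal is possible.
- **Grade 4:** the event requires removal, or "the subject is at immediate risk of death, even if not related to the implant(s".

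A paragraph on expedited reporting by judgement follows. It covers important events that are not immediately life-threatening and do not lead to death or hospitalization, but that "may require intervention to prevent one of the other outcomes listed in the definition above". Then comes the seriousness rule: "An Adverse Event that is of Grade 3 or Grade 4 will be considered a serious adverse event (SAE". Reporting hangs on it: "All serious adverse events (SAEs) should be reported immediately to the Sponsor". The sponsor then reports SAEs to the regulatory authorities.

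Protocol 11.1.3 adds a rule for one kind of surgery: "A non-elective removal is any removal other than an elective removal and is considered an SAE". An elective removal is not an SAE.

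Overall success has four components (Protocol 5.1.2 and 5.2.2; SAP 7.8.2.1). The adverse event component in the SAP reads "No serious, implant or implant/surgical procedure associated adverse event". The SAP text available does not define serious. SAP 7.8.2.8 plans life-table analyses of Grade 3 or 4 events, and a summary of serious adverse device effects if available.

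**The concern.** The expedited-reporting paragraph reads as though an outcome-based definition of seriousness stood just before it. None does; what stands there is a severity scale. Severity describes how intense an event is. The outcomes the paragraph names describe what the event led to. The two often coincide but need not, and the protocol supplies only the first as its general test.

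Two things depend on the answer. SAE status is what makes an immediate report to the sponsor mandatory. It also decides one of the four components of overall success. Protocol section 12 provides no data review committee, so classification rests on the investigator and the sponsor. Protocol 13.1.3 plans to show clinical outcomes beside those of the two-level IDE study, and a reader of those tables needs to know what serious means here.

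**Working it through.** The plan states no figure on this point, so there is none to reproduce. The check is mainly a comparison of texts, with simple arithmetic for scale.

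**1. What could the reference to a definition above mean?** Only the four grades precede it.

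- Hospitalization occurs once, in Grade 3, as something that may be required, and joined to a marked limitation that persists despite symptomatic therapy.
- Immediate risk of death occurs in Grade 4.
- Death as an outcome occurs in no grade.
- None of these is presented as an outcome that makes an event serious.

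**2. Trace a lower-grade event through the rules.** Take, as an illustration, an implant-related event not defined in the WHO scale. The subject is admitted, the symptoms interfere with routine activity, they settle with symptomatic therapy, and no implant is removed.

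- Grade: it fits the Grade 2 wording. It does not fit Grade 3, which needs limitation despite symptomatic therapy.
- General SAE rule in 11.1.1: not met.
- Removal rule in 11.1.3: not met, since nothing is removed.
- Mandatory immediate report: not triggered.
- Adverse event component of overall success: passed.

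**3. What still catches the event?**

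- 11.1.1 allows expedited reporting by judgement.
- 9.18 requires immediate reporting of any cancer event, whatever its grade.
- 11.2 makes all adverse events reportable, promptly, with an assessment of seriousness, and has sponsor safety staff review them promptly.
- Overall success can still fail on the NDI, on neurological status, or on a surgery classed as a failure (revision, non-elective removal, supplemental fixation).

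The first three bear on reporting. None of them changes the adverse event component of overall success.

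**4. Scale.** Input: n = 30 subjects (Protocol 8.1; SAP section 6). If k subjects pass every other component and have such an event, overall success is higher by 100 × k/n percentage points than under an outcome-based rule:

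- k = 1: 100 × 1/30 = 3.3
- k = 2: 100 × 2/30 = 6.7
- k = 3: 100 × 3/30 = 10.0

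The unit is the subject, not the event: two such events in one subject still move the rate by one step. SAP 7.1.3.1 excludes subjects who were not treated or had no postoperative follow-up. A smaller evaluable denominator would enlarge the step, but the documents give no expected number.

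The documents do not give the rate p of affected subjects. For assumed values, the chance of at least one in 30 is 1 − (1 − p)^30:

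| Assumed p | (1 − p)^30 | Chance of at least one |
|---|---|---|
| 1% | 0.740 | 26% |
| 3% | 0.401 | 60% |
| 5% | 0.215 | 79% |
| 10% | 0.042 | 96% |

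These rates are illustrative. An affected subject must have an implant-related event with such an outcome, graded 1 or 2, and meet all other components, so small values are the natural ones to consider.

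**The case against.** The strongest reply is that this is a loose cross-reference in a usable rule. Grade 3 or 4 is a clear criterion, and the SAP uses the same grades in its adverse event tables. Hospitalization, risk of death and implant removal all sit in the grades above and could be what the reference means. The judgement paragraph exists precisely to pick up events outside the rule. A fatal event would normally have put the subject at immediate risk of death, and so reach Grade 4. The WHO scale comes first for the events it defines, and its treatment of admission or death is not reproduced in the documents. Overall success is secondary, no statistical conclusion is drawn from it, and the study has no hypothesis.

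Much of this stands, and it limits what may be claimed. A reader might infer more in four places, and the documents do not support it:

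- **That an event is serious only if it is Grade 3 or 4.** The text says such events will be considered serious, without the word only, and 11.1.3 names non-elective removal separately. That rule is weak evidence of a conflict, however. Grades 1 and 2 exclude a need for removal, so a required removal already belongs in Grade 3 or 4 and the two sections largely agree.
- **That the outcomes are never mentioned.** Hospitalization and risk of death do appear, but as features of grades, not as seriousness criteria.
- **That a lower-grade event goes unreported.** It loses the mandatory SAE trigger; the other reporting rules remain.
- **That every such event raises the success rate by 3.3 points.** It does so only for a subject who meets everything else.

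What the objection does not remove is the gap itself. Discretion to expedite does not classify the event, and no reporting safeguard alters the success rule. A possible referent inside Grade 3 does not help an admitted subject whose event fits Grade 2.

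**Conclusion.** The point holds in a limited form. The protocol's one general test for seriousness is a severity grade, and its reference to listed outcomes has no list of seriousness outcomes behind it. Followed as written, a lower-grade event that led to hospitalization, or needed intervention to prevent such an outcome, is not automatically an SAE. It has no mandatory immediate report unless another rule applies. If implant related, it leaves overall success untouched unless another component fails.

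The effect is at most 3.3 percentage points per affected subject at n = 30. How many subjects would be affected cannot be derived from the documents. The grade rule also works in the other direction: a severe implant-related event with none of these outcomes counts as serious and fails the subject. One should therefore not infer that the rule as a whole is lenient, only that it misses one class of event. The conclusion rests on the protocol's own four grades; for events graded on the WHO scale the documents do not show what would happen.

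This is a cheap and worthwhile correction to a safety term, not a threat to the primary metal concentration results.

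**What to change.** - **Protocol 11.1.1:** define an SAE as an adverse event of Grade 3 or 4, or any adverse event that results in death or hospitalization or needs intervention to prevent these. The preceding paragraph already names these outcomes. Point its cross-reference at this definition.
- **Protocol 11.1.3:** reconcile the removal rule with the definition, so that it is clear whether removal status is an application of it or a separate criterion.
- **SAP 7.8.2.1 and 7.8.2.8:** cite the protocol definition, so that overall success and the adverse event tables use one meaning of serious.
- **Reporting:** keep the count based on Grade 3 or 4 alone as a supportive row. This preserves the rule as now written for comparison. Do not assume which definition the IDE study used; the documents do not say.

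The cost is protocol and SAP wording, a few more SAE reports and possibly a slightly lower overall success rate. 11.2 already requires every adverse event to be reported with an assessment of seriousness, so no new reporting step is needed, provided the report records the qualifying outcome.

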#### Medtronic Controlled Information

reports should be followed promptly by detailed, written reports. The immediate and follow-up reports should identify patients by unique code numbers assigned to the study subjects rather than by the subjects' names, personal identification numbers, and/or addresses. The investigator should also comply with the applicable regulatory requirement(s) related to the reporting of unexpected serious adverse drug reactions to the regulatory authority(ies) and the IRB.

The follow-up report should give full details of the experience, including an assessment of the relationship to the test article(s), and will be sent to the Sponsor promptly. SAEs will then be reported to regulatory authorities by the Sponsor.

### 11.1.2 Assessment of Related Adverse Events

The relationship between an AE and the implant/procedure will be assessed by the Investigator, and by the Sponsor on the basis of the following definitions:

**Implant Associated/Related:** AE for which there is a reasonable possibility that the event may have been caused by one or more components of the implant.

**Surgical Procedure Associated/Related:** AE for which there is a reasonable possibility that the event may have been caused primarily by the surgical procedure.

**Implant/Surgical Procedure Associated/Related:** AE for which there is a reasonable possibility that the event may have been caused by both the implant(s) and the surgical procedure.

**Undetermined:** AE for which sufficient information is not available at the time of the event to determine causality.

**Not Related (NR):** AE for which sufficient information exists to indicate that the etiology is unrelated to the implant(s) or surgical procedure.

All AEs are required to be entered in a timely fashion, into the EDC on the Adverse Event Electronic Case Report Form and each will be classified according to the aforementioned criteria. The Investigator should pay particular attention to the subject's postoperative neurological evaluations. It is important that any new, significant neurological deficits be reported as an AE. In addition, in the event that a subject experience an AE involving a malignancy, the investigator should make every attempt to provide a pathology report describing the location or the tumor; the histopathology of the tumor; other comorbid medical diagnosis; and the age of onset, gender, and ethnicity of the subject. Any information regarding the subject's family history of cancer should also be provided, if available. Any subject with a malignancy will be followed until the subject completes the study. Periodic updates should be provided by the clinical site to the Sponsor.

---

#### Medtronic Controlled Information

# Prestige LP™2 Metal Concentration Clinical Investigation Plan

MDT16060SD1701

Version 6.0, 08-JUL-2019

Page 34 of 46

Medtronic

## 11.1.3 Secondary Surgical Interventions

Some AEs or treatment failures may lead to a secondary surgical intervention at an operated index level. Information on the types of secondary surgical interventions is provided in the section below. Secondary Surgical Interventions will be classified by Medtronic. All patients undergoing a secondary surgical intervention at any operated index level will be followed.

- **Revision:** A procedure that adjusts or in any way modifies either one or both of the original implant configurations (e.g., adjusting position of the original configuration, removal with replacement with the same type of study implant). A revision will be classified as a treatment "failure".**Removal:** A procedure that removes one or more components of the original implant configuration without replacement with the same type of trial implant. Removals will be classified as either elective or non-elective. An elective removal is a procedure that removes the Prestige LP™ Cervical Disc(s) at the discretion of the investigator and/or the patient. An elective removal will not be classified as a treatment "failure." An elective removal is not considered an SAE. A non-elective removal is any removal other than an elective removal and is considered an SAE and will be classified as a treatment "failure."

NOTE: In the event that an implant requires a removal (explant), specific information and instructions are to be followed for this process. The instructions and information regarding the process is provided in the "Procedure for Retrieval, Handling and Packaging" included as an attachment to this protocol in **Appendix II**. All explanted devices will be analyzed along with histological evaluation of any retrieved peri-prosthetic tissue under the Post-approval Device Failure study (Explant Analysis) for the two-level indication.

- **Supplemental Fixation:** A procedure at the involved level(s) in which additional spinal devices not approved as part of the protocol are placed. A supplemental fixation will be classified as a treatment "failure."
- **Reoperation:** Any surgical procedure at the involved level(s) that does not remove, modify, or add any components and is not considered a removal, revision, or supplemental fixation. A reoperation, elective removal or other surgical procedure will not be classified as a treatment "failure."
- **Other:** Any surgical procedure not classified as a revision, removal, supplemental fixation or reoperation.

## 11.2 Reporting of Adverse Events

AE reporting processes will be carried out in compliance with the protocol, the governing IRB, and the requirements of FDA and other applicable authorities.

All adverse events will be considered reportable for this study.

---

### Medtronic Controlled Information

This document is electronically controlled

056-F275, vA Clinical Investigation Plan Template

# Prestige LP™2 Metal Concentration Clinical Investigation Plan

MDT16060SD1701

Version 6.0, 08-JUL-2019

Page 35 of 46

Medtronic

Adverse events must be recorded in the subject's medical record and on the Adverse Event and/or Device Deficiency eCRF and promptly reported to Medtronic. IRB/EC reporting must be completed in accordance with the policies of the governing IRB/EC.

It is the responsibility of the Investigator to identify the occurrence of adverse events and device deficiencies and to ensure the required information is accurately documented on the eCRF.

Reports of adverse events and device deficiencies will include the following information, at a minimum:

- Date of event
- Diagnosis or description of the event
- Assessment of the seriousness and relationship to the device and/or surgical procedure
- Treatment provided
- Outcome and date of resolution

The clinical course of each adverse event must be followed until resolution, subject discontinuation from the study or last study follow up visit, whichever comes first. "Not resolved" adverse events and device deficiencies must be assessed at each protocol required visit, and new or updated information must be documented on the Adverse Event and/or Device Deficiency eCRF and promptly reported to Medtronic and, if applicable, to the IRB. At time of study exit the status of all unresolved Adverse Events should be evaluated and should reflect subject' status at time of study exit.

If necessary, the Investigator may report to the sponsor initially by telephone or e-mail and follow-up with completed eCRFs and, upon request of Medtronic, de-identified source documentation regarding the event (e.g., physician/nurse notes or summaries) should be provided to Medtronic.

Medtronic safety personnel will promptly review all reported adverse events and device deficiencies and if necessary request clarification and/or additional information from the Investigator. In addition, aggregate safety data will be reviewed and analyzed to identify potential safety issues, signals, and trends at minimum, annually after the first subject is enrolled.

## 12 Data Review Committees

Due to the nature of this study, no data review committees will be convened for this study.

### Medtronic Controlled Information

This document is electronically controlled

056-F275, vA Clinical Investigation Plan Template

